7.2 Statistical Methods

Specific statistical methods that will be used to evaluate each primary and secondary hypothesis or objective are described in this section.

The incidence, prevalence and recurrence rates of cardiac and lung complications (Objectives O1 and O3) will be summarized using confidence intervals on proportions. These rates will be determined at various time points (e.g., fetus, neonate and age 2.5 years); and will also be calculated in various subgroups such as Groups IIA and IIB or those children with and without certain cofactors (e.g., receiving drugs for treatment of HIV virus).

The primary hypotheses (H1 and H2) of comparing complication rates at specific time points in children with and without HIV-infection (Groups IIA and IIB) will be evaluated using the Mantel-Haenszel chi-square test stratifying on important potentially confounding variables such as IVDA of the mother. If there are several factors that need to be adjusted for simultaneously, a logistic regression analysis will be used to compare the rates with the factors as independent variables in the model along with an indicator variable representing group assignment. Similar analyses also apply to Hypotheses H3 and H4.

The persistence of cardiac abnormalities from the fetus to the neonate (Hypothesis H5) can be evaluated using McNemar's chi-square. If the abnormality is measured using a continuous variable (e.g., wall thickness from an echocardiogram), a paired t test or Wilcoxon signed rank test can be used.

To determine which cofactors are associated with cardiac or pulmonary abnormalities (Hypotheses H6 and H7), a logistic regression analysis will be done.

To determine whether diagnostic methods are able to detect cardiac or pulmonary disease before signs or symptoms appear in HIV-infected children (Objective O2), the sensitivity, specificity and positive and negative predictive values of each method will be determined. In order to determine the optimal cut-point for a diagnostic measure, a receiver operating characteristic (ROC) analysis will be performed (Metz, 1978). Combinations of diagnostic methods that may better detect disease will be evaluated using logistic regression analysis. The specific diagnostic methods likely to be of value are: LDH or PO_2 (or $A-aO_2$) for PCP, IgG for lymphoproliferative lung disease, echocardiogram measures (e.g., fractional shortening) for ventricular disease EKG measures (e.g., PR interval) for detecting arrhythmia, and DTPA for detecting early lung disease.

To evaluate whether PCP accelerates the rate of lung function decline, (Objective O4), the decline in children with and without PCP can be compared using an unpaired t test or a Wilcoxon rank sum test. More elaborate longitudinal data analyses are described in Section 7.3. To determine whether PCP shortens the life span of HIV-infected children with chronic lung disease (Objective O4), a survival analysis will be performed. Detailed discussion of such an analysis is described in Section 7.4.

All hypotheses and objectives referring to HIV-infected children apply to children in Groups I and IIA.

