2.3 Secondary Hypotheses and Objectives

Hypotheses

- H3. The incidence of cardiovascular disease in HIV-infected children is increased with EBV and CMV infections.
- H4. The incidence of lymphoproliferative interstitial lung disease in HIV-infected children is increased with EBV infection.
- H5. HIV associated abnormalities of cardiovascular anatomy or function in the fetus persist into the neonatal period.
- H6. Identifiable cofactors of HIV-infection are associated with alterations in cardiovascular anatomy and function in the neonatal infant and child and include:
 - a. Pulmonary/systemic bacterial/viral infection
 - b. Altered immune system
 - c. Primary treatment of HIV-infection
 - d. Perinatal events (including intrauterine growth retardation, drug exposure, or infection) and neonatal illness
 - e. Growth failure
- H7. Identifiable cofactors of HIV-infection are associated with specific pulmonary** complications in the neonatal infant and child and include:
 - a. Altered immune system
 - b. Primary treatment of HIV-infection
 - c. Perinatal events (including intrauterine growth retardation, drug exposure, or infection) and neonatal illness
 - d. Growth failure

Objectives

- 02. To determine whether pulmonary and cardiovascular disease associated with vertically transmitted HIV infection is detectable with sensitive diagnostic methods before clinical signs and symptoms appear.
- 03. To estimate the recurrence rate of PCP.
- 04. To determine whether PCP accelerates the rate of decline of lung function and shortens the life span of HIV-infected children with chronic lung disease.

* Specific cardiovascular complications related to these hypotheses for the fetus are a-h, and for the postnatal infant and child are b-i:

- a. Altered umbilical blood flow profile
- b. Structural heart disease
- c. Altered myocardial performance
- d. Pericardial effusion with and without hydrops
- e. Arrhythmias
- f. Altered chamber size and wall thickness
- g. Cardiac valvular insufficiency or obstruction
- h. Cardiac tumors or masses
- i. Endocarditis (active or healed)

** Specific pulmonary complications related to these hypotheses are:

- a. Upper respiratory infection (rhinitis, pharyngitis, otitis, sinusitis)
- b. Fungal pulmonary infection
- c. Viral pulmonary infection
- d. Bacterial pulmonary infection
- e. Mycobacterial pulmonary infection
- f. Pneumocystis carinii pneumonia
- g. Lymphoproliferative lung disease
- h. Other interstitial lung diseases

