Before 1981, PCP in the U.S. was reported predominantly in children with primary immunodeficiency or secondary immunodeficient states, i.e. neoplastic disease (Perera et al, 1970). In 1988, 33% of all U.S. AIDS cases (adult and pediatric) reported at least one episode of PCP. Morbidity and mortality from PCP is high with progression to hypoxic respiratory failure and mechanical ventilation noted in 25% of adults (Maxfield et al, 1988) and in greater than 50% of children (Marolda et al, in press). The most common opportunistic infection reported in children with HIV infection is PCP and it appears to have an especially fulminant course in those less than 1 year of age (Rogers et al, 1987). In children with AIDS, PCP ranks second only to LIP as the most frequently encountered pulmonary disease. Pneumocystis carinii, identified as a protozoan because of its response to antiprotozoan therapy, also has qualities of a fungus (Anderson and Hughes, 1987). Neither the route of transmission nor habitat of Pneumocystis carinii is defined although vertical transmission is suspected in some cases. Pathologically, the organism appears to be primarily restricted to lung tissue (attached to alveolar epithelial type II cells) although in rare cases reticuloendothelial involvement, blood borne infections, skin infections, and otitis media have been reported (Rahimi, 1974). Organisms have been demonstrated in sputum, bronchial washings, tracheal aspirates, and lung biopsies of symptomatic patients. The clinical manifestations of PCP in children have been distinguished from other pulmonary disease, i.e. LIP, by severity of hypoxemia, higher alveolar - arterial oxygen gradients, A-aDO₂, elevated serum lactate dehydrogenase levels, rapidity of disease progression with tachypnea, fever, characteristic diffuse interstitial infiltrates on chest radiograph, and lack of digital clubbing (Rubinstein et al, 1986). In adults with HIV infection, PCP may have a more insidious onset with symptoms of fever averaging 7 weeks and cough or dyspnea averaging 3 weeks before diagnosis (Engleberg et al, 1984).

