7.3 Longitudinal Analyses

Various clinical and laboratory measurements will be made periodically during the 2-1/2 to 4-1/2 year follow-up period. Most longitudinal methods typically require balanced data (i.e., no missing observations) which is unlikely to be true in this study. Alternatively, meaningful summaries of the longitudinal experience for each patient will be developed such as the rate of change from baseline, and these summary measures can be compared between groups using t tests or Wilcoxon rank sum tests.

Changes in continuous measurements (e.g., PaO₂) over time will be compared by calculating a slope over time for each patient and comparing mean slopes between groups. The validity of the linearity assumption will be investigated. Due to varying lengths of follow-up caused by staggered enrollment, termination of the study, dropouts, and mortality, there will be different numbers of measurements between subjects and inequalities in the precision of estimates of individual slopes, so a weighted mean slope will be used to determine group means and variances. These weighted mean slopes can be compared between groups using a weighted regression model which can also include covariates from baseline.

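### Section 7.2 assigns PCP recurrence (O3) to a proportion with no risk set, clock or censoring, so short follow-up after the first episode pulls the estimate down

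*Protocol*

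**What the plan says.** Objective O3 in Section 2.3 reads: "To estimate the recurrence rate of PCP". Section 7.2 presents itself as the place where each objective receives its method: "Specific statistical methods that will be used to evaluate each primary and secondary hypothesis or objective are described in this section". For O3 that method is: "The incidence, prevalence and recurrence rates of cardiac and lung complications (Objectives O1 and O3) will be summarized using confidence intervals on proportions". The next sentence adds: "These rates will be determined at various time points (e.g., fetus, neonate and age 2.5 years"). The nearest statement of population, at the end of the section, is: "All hypotheses and objectives referring to HIV-infected children apply to children in Groups I and IIA".

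Section 7.2 sends the life-span part of O4 to survival analysis, with a pointer to Section 7.4. It gives O3 no such pointer. Section 7.1 says time-to-event analysis will be the main type of analysis. Section 7.4 applies it to morbidity and mortality outcomes and credits it with coping with unequal follow-up, but mentions neither O3 nor recurrence. Section 7.3, writing about slopes, expects "varying lengths of follow-up caused by staggered enrollment", along with study termination, dropout and death.

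**The concern.** A recurrence can be observed only between the first episode and the end of that child's observation. An estimate therefore needs three things that Section 7.2 does not give for O3: who is at risk, when the clock starts, and what happens when observation stops early.

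Without them, the stated method divides children seen to recur by children who had a first episode. A child whose first PCP comes a few months before follow-up ends then counts the same as one watched for years without recurrence. The result mixes recurrence risk with length of observation. The confidence interval reflects sampling error around that mixture and gives no warning of the shortfall.

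**Working it through.** **1. The plan's own interval.** Section 4.2.2 uses a half-width of 100 × 1.96 × √(p(1−p)/n).
- n = 200, p = 0.5: 100 × 1.96 × √(0.25/200) = 6.93, stated as 6.9%.
- n = 200, p = 0.25: 100 × 1.96 × √(0.1875/200) = 6.0, stated as 6.0%.

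All ten rows of Table 4 reproduce. The interval formula is not in question; the issue is what the interval is centred on.

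**2. Children available for O3.** Take the 25% PCP illustration for 200 Group I children (Section 4.2.2) and the 24% PCP rate (Table 6) for 120 Group IIa children (Section 4.2). Then 0.25 × 200 + 0.24 × 120 = 50 + 28.8 = 78.8, about 79 first episodes. With n = 79 the half-width is 8.8 points at p = 0.20 and 10.1 points at p = 0.30.

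**3. Effect of short follow-up alone.** The protocol gives no recurrence risk, no PCP fatality and no distribution of follow-up after a first episode, so these are assumed:
- two-year recurrence risk R of 40% or 20%, with constant hazard λ = −ln(1−R)/2;
- follow-up after the episode uniform from 0 to F years and independent of recurrence;
- no deaths.

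F = 4.5 is the maximum follow-up in Section 7.3. F = 6.7 is the 6 2/3-year Phase II in Appendix 1. F = 2 stands for first episodes late in follow-up.

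The expected crude two-year proportion is [(2 − R/λ) + (F − 2)R] / F.

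For R = 0.40, λ = 0.2554 and 2 − R/λ = 0.434:
- F = 4.5: (0.434 + 2.5 × 0.40)/4.5 = 31.9%
- F = 2: 0.434/2 = 21.7%

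| Assumed two-year risk | F = 2 | F = 4.5 | F = 6.7 |
|---|---|---|---|
| 40% | 21.7% | 31.9% | 34.5% |
| 20% | 10.4% | 15.7% | 17.1% |

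At 40% the shortfalls are 18.3, 8.1 and 5.5 points. The first exceeds the half-width of about 9 to 10 points; the other two lie within it.

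**4. What deaths add.** With F = 4.5, R = 40% in survivors and all first episodes in the denominator:
- 25% assumed first-episode fatality: the crude figure is 23.9%; the cumulative incidence with death competing is 0.75 × 40 = 30%.
- 50% assumed fatality: the crude figure is 15.9%; the cumulative incidence is 0.50 × 40 = 20%.

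The ratio of crude to correct is the same each time: 31.9/40, 23.9/30 and 15.9/20 are all about 0.80. In this setting first-episode deaths change the quantity being estimated. The downward bias comes from short follow-up.

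**The case against.** The strongest reply is that Sections 7.1 and 7.4 already make time-to-event analysis the main method for morbidity outcomes, and Section 7.1 lists PCP among the possible primary outcomes. On this view the proportion in Section 7.2 is only a summary. That stands to the extent that the proportion is not clearly the only analysis. But Section 7.2 is where methods are matched to objectives. It names O3 and assigns it a proportion, while directing part of O4 to survival analysis, so an analyst following it would compute a proportion.

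A second reply is that the denominator is undefined and may be left to a later analysis plan. A reader might infer that children who die in their first episode stay in the denominator, and that recurrence is therefore understated in proportion to fatality. The documents do not support this. No denominator is given, and a proportion among survivors fits the wording as well. Counting those deaths is also legitimate when death is treated as a competing event. Limiting the analysis to children with a full two-year window would remove the administrative part of the follow-up bias. The plan does not say this, and under F = 4.5 it would set aside 2/4.5 = 44% of first episodes.

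Third, a reader might infer that the fetus, neonate and age 2.5 list fixes a clock for PCP recurrence. It is introduced as an example, is shared with O1, and matches the columns of the cardiac Table 5, so it fixes nothing for O3.

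Finally, follow-up may be fairly long. Appendix 1 ends Group II recruitment in January 1994 and follow-up in January 1997, about three years later. That runs from enrolment, however, and a first PCP can occur at any point within it.

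**Conclusion.** The point holds in limited form. The method named for O3 takes no account of unequal follow-up after the first episode and conflicts with the approach of Sections 7.1 and 7.4. No stated number is wrong.

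Under the assumptions above, short follow-up lowers an assumed 40% two-year risk to about 32% (F = 4.5) or 22% (F = 2), a relative loss of about 20% or 46%. With F = 6.7 it is about 14%. The direction does not depend on the assumed values as long as some children leave observation early and are counted as non-recurrent; the size does. The documents do not support a figure for bias from first-episode mortality.

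O3 is a secondary objective of estimation with no test attached, but Section 2 calls the secondary objectives scientifically as important as the primary hypotheses. The change is worth making.

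**What to change.** In Section 7.2, take O3 out of the sentence on proportions and refer it to Section 7.4, specifying:
- **Risk set:** children with a first PCP.
- **Clock:** from the diagnosis date of that episode, or from a stated recovery date in those who survive it.
- **Censoring:** at end of follow-up, with death as a competing event. Section 7.4 names Kaplan-Meier curves, so a cumulative incidence estimate has to be added.
- **Report:** cumulative incidence of recurrence at fixed times, for example 6, 12 and 24 months, with confidence intervals, and first-episode fatality separately.

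The cost is somewhat wider intervals. A working rule is also needed to separate a recurrence from a continuing episode, because Table 13 defines PCP by detection of organisms and does not say when an episode ends. Section 7.1 warns that exact event times may be unknown, so the rule should also say which date is used when onset is uncertain.

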5.1.3 Immunologic/Virologic Assessment of Infants in Group I

Infants in Group I will be those documented with vertical transmission of HIV-infection who are over 28 days of age. Approximately 200 infants and children total will be enrolled at the five centers. The time sequence of visits and immunologic/virologic tests are contained in Table 8. Although patients will be seen in clinic for other components of this study, the immunologic/virologic testing of Group I will be less intense and, in general, tests will be performed on an annual basis. The types of tests selected for Group I patients are those which will permit correlation of cardiac and pulmonary condition with HIV disease state as reflected in the degree of immunodeficiency and the extent of coinfection with CMV and EBV. Western Blot banding patterns have been associated with stages of HIV infection. For example, the loss of antibody to p24 Ag on Western Blots has been associated with advanced HIV disease (Falloon et al, 1989). Serum immunoglobulin (Ig's) are known to be a very sensitive index of HIV-infection in infants and children, frequently rising well beyond the normal ranges in early disease and falling in terminal disease (Falloon et al, 1989). Leukocyte markers (CD3, CD4, and CD8 cell counts) are perhaps the most sensitive in vitro assessment of the stage of HIV-infection, with CD4 cell counts of less than 200 indicative of a precarious state of health (Falloon et al, 1989). Delayed hypersensitivity skin tests (DHST) are a reliable means of testing specific T-cell recall of antigens, and can be used to determine anergy. Testing will be performed on children over 1 year of age. Cultures and serologic tests for CMV and EBV can be utilized in conjunction with tests of cardiac and lung function to determine the role these viruses play in accelerating the complications of HIV-infection. For Group I patients, these tests will be obtained when the patients are symptomatic, according to the schedule outlined in Table 8. Listed in Table 8 are clinically warranted tests (CBC, LDH, ESR, stored serum) which will be obtained on a 12 month schedule, except when intercurrent or chronic disease occurs. When patients develop intercurrent or chronic illness, these tests will be repeated (six times per year estimate); in addition, serum Ig's, lymphocyte subsets (CD3, CD4, CD8), DHST's-70°C serum (storage) will be repeated unless performed within 2 month's; CMV and EBV cultures will be obtained for chronic illness if previous cultures were negative. In addition, viral cultures for influenza, parainfluenza, RSV, and adenovirus

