5.2.2 Scheduled Pulmonary Evaluation

The schedule of routine pulmonary evaluation is constructed to gather baseline data from patients prior to illness and to monitor the patients at an interval expected to allow early detection of pulmonary complications. The median age of diagnosis of HIV is 13 months, with the median age of onset of lymphoproliferative lung disease at 17 months. A relatively frequent interval of monitoring (every 3 months), will allow early detection of these pulmonary complications. Less invasive studies constitute this screening battery. Clinical illness prompts initiation of the algorithms for evaluation of an intercurrent illness or chronic lung disease. Questionnaires (Qst) were developed to follow the history of pulmonary symptoms, clinical course, and clinical care for Group I and Group II. The perinatal form is discussed in Section 5.2.1. The environmental Qst is completed at entry into the study and with each change of household during the study for both groups. The basic respiratory Qst is completed at entry into the study for Group I patients. The interval respiratory Qst is completed each visit following enrollment. During each patient's first year, the patient is seen every 3 months; during the remainder of this study, the patient is seen every 6 months. A physical examination form will be completed at all of these visits. The respiratory rate is always recorded during sleep or quiet breathing. Oxygen saturation (SpO₂) will be performed at every visit as outlined in Section 5.2.4.4. Pulmonary function testing will be performed biannually on Group I and II patients. Details of pulmonary function testing for specific age groups are found in section 5.2.4.4. A DTPA clearance scan will be performed on all patients at six-month intervals. Scans will be discontinued after 18 months in HIV negative patients (Group IIb). (DTPA studies were discontinued on February 10, 1993 on the recommendation of the Steering Committee).

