patient remains symptomatic despite two weeks of appropriate antibiotic therapy, an open lung biopsy will be performed. We will wait up to five days after instituting empiric antibiotic therapy prior to performing a bronchial lavage or an open lung biopsy on patients with focal consolidation who are hypoxemic. An open lung biopsy will be performed within 24 hours if the radiograph shows diffuse interstitial lung disease with a negative BAL and the patient is hypoxemic.

Bronchoscopy/BAL

Patients will have bronchoscopy and bronchoalveolar lavage (BAL) according to the algorithm (Figure 1). BAL will be performed on hypoxemic patients or those unresponsive to appropriate treatment for up to 2 weeks or experiencing worsening symptoms. The fluid will be handled as per Section 5.2.4.6. The lavage should preferably be done within 48 hours of the documentation of hypoxemia or within 48 hours of starting TMP-SMX.

Open Lung Biopsy

An open lung biopsy will be done if a bronchial lavage is non-diagnostic or if treatment has failed despite a diagnostic bronchial lavage. The specimen will be processed as outlined in Section 5.2.4.7. All patients who undergo open lung biopsy for any reason will have a BAL the same day so that direct comparison of the value of these methods may be made and recommendations for their use in the future may be clarified.

Follow-up

Patients with intercurrent illness or chronic lung disease will continue to receive the scheduled follow-up after the illness has resolved or stabilized. In patients who are hospitalized, a discharge evaluation will be made. This will include:

- a) Physical examination
- b) Chest radiography
- c) Oxygen saturation and/or arterial blood gas

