5.2.4.2 Chest X-rays

Rationale:

Chest x-rays obtained at intervals provide an opportunity to detect pulmonary infiltrates at an early stage and to record the radiologic response to treatment or the progression of the pulmonary disease in the absence of a response to treatment.

Frequency of Study:

Chest x-rays will be routinely performed at enrollment and months 12, 24, 36, 48, 60 and 72 on Group I patients; months 3, 12, 18, 30, 42, 54, 66 and 78 on Group IIa patients; and months 3, 12, 18 for Group IIb. Chest x-rays will also be performed when clinically indicated as part of diagnosis and treatment of intercurrent respiratory tract illnesses; the latter will be charged to the study. (Prior to 6/10/93, CXR test schedule for Group I and Group IIa was month 3, 9, 18, 30 and 42; Group IIB was month 3, 9 and 18).

Method:

Inspiratory chest x-rays will be obtained in frontal and lateral planes, using routine techniques as performed at the individual centers.

5.2.4.3 Determination of Oxygenation and Pulmonary Gas Exchange by Pulse Oximetry and Arterial Blood Gas Analysis

Rationale:

Arterial blood gas analysis is the most sensitive laboratory method for detecting abnormalities in pulmonary gas exchange and for monitoring gas exchange adequacy over time. However, this is an invasive laboratory test. Recently, it has been possible to estimate the adequacy of oxygenation in small infants by pulse oximetry (SpO_2), a non-invasive, continuous estimate of hemoglobin oxygen saturation (Fanconi, 1988; Praud et al, 1989). We propose to monitor oxygenation with this test and to reserve arterial blood gas analysis for instances in which pulse oximetry is either indeterminate (see interpretation), inaccurate (e.g., methemoglobinemia, skin color) or clearly below the normal range.

Frequency of Study:

Pulse oximetry will be performed at each study interval, i.e. every three months during the first year and twice yearly for the remainder of the tenure of the project. Arterial blood gas analysis will be performed when SpO_2 is abnormal in order to determine the extent of the defect in oxygenation and to define whether ventilation, i.e. carbon dioxide elimination, is also impaired. During clinic visits for evaluation of intercurrent illness, arterial blood gas analysis, rather than SpO_2 will be performed.

Method:

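### The tests that 7.2 names for pre-symptomatic PCP and early lung disease (PO2 or A-a gradient, LDH, DTPA) are mostly not collected in a way that can answer O2

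*Protocol*

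**What the plan says.** Objective O2 (Protocol 2.3) asks whether heart and lung disease "is detectable with sensitive diagnostic methods before clinical signs and symptoms appear". Section 7.2 takes this up with the words "To determine whether diagnostic methods are able to detect cardiac or pulmonary disease before signs or symptoms appear in HIV-infected children (Objective O2"), and answers it by stating that "the sensitivity, specificity and positive and negative predictive values of each method will be determined", with ROC analysis for cut-points. It then lists markers: "The specific diagnostic methods likely to be of value are: LDH or" PO2 (or the A-a gradient) for PCP, IgG for lymphoproliferative lung disease, echocardiogram and ECG measures for the heart, and DTPA for early lung disease.

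The collection rules are elsewhere:

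- **Arterial gas.** Section 5.2.4.3 plans to "reserve arterial blood gas analysis for instances in which pulse oximetry is either indeterminate", inaccurate or clearly low. At illness visits a gas replaces oximetry.
- **PCP reference test.** Table 13 requires organisms in BAL fluid or open lung biopsy. Under 5.2.3.1, "BAL will be performed on hypoxemic patients or those unresponsive to appropriate treatment for up to 2 weeks or experiencing worsening symptoms".
- **LDH.** In Group I (5.1.3) it is "obtained on a 12 month schedule, except when intercurrent or chronic disease occurs". In Group II (5.1.4) the interval is 6 months, again with repeats at illness.
- **DTPA.** Section 5.2.2 records that "DTPA studies were discontinued on February 10, 1993 on the recommendation of the Steering Committee".

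**The concern.** O2 is about children who are still well. A test can inform it only if it is done in well children regardless of its own result, and if disease is confirmed in a way that does not lean on that result. For the PCP markers the protocol's own rules meet these conditions poorly. PaO2 is mostly measured in children already ill or already flagged by oximetry. Low oxygenation helps decide who is lavaged. LDH is seldom drawn shortly before an acute illness unless that illness has begun. If 7.2 were carried out with whatever PO2 and LDH values exist, accuracy among sick or pre-screened children could be reported as early detection. Section 2 says the secondary objectives are scientifically as important as the primary ones, so this is worth settling.

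**Working it through.** The protocol gives no sample size or precision for O2, so there is no figure to reproduce. The check compares the rules and adds two illustrations.

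**1. Who has a PaO2.** Tables 8 to 11 and Table 14 schedule no arterial gas. The Table 14 footnote ties a gas to saturation below 96%, or to 96-97% if clinically indicated. Section 5.2.4.3 also allows the gas to be skipped in some closely followed children whose examination, sleeping respiratory rate and chest film are normal. A symptom-free child with normal oximetry therefore contributes no PaO2. Specificity and negative predictive value need such children, so for PaO2 before symptoms they cannot be estimated.

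**2. Verification that depends on the index test.** Let Se and Sp be the true values, and v+ and v- the shares of hypoxemic and non-hypoxemic children who are lavaged. If, given the oxygenation result, lavage does not depend on disease:

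- apparent sensitivity = Se·v+ / [Se·v+ + (1-Se)·v-]
- apparent specificity = Sp·v- / [Sp·v- + (1-Sp)·v+]

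All values here are assumed: Se 0.60, Sp 0.90, v+ 0.90.

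| v- | Apparent sensitivity | Apparent specificity |
|---|---|---|
| 0.90 | 0.54/(0.54+0.36) = 0.60 | 0.81/(0.81+0.09) = 0.90 |
| 0.30 | 0.54/(0.54+0.12) = 0.82 | 0.27/(0.27+0.09) = 0.75 |
| 0.10 | 0.54/(0.54+0.04) = 0.93 | 0.09/(0.09+0.09) = 0.50 |

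This shows direction only. The protocol does not give v+ or v-.

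**3. Coverage of scheduled LDH.** Section 3.2.1 describes acute onset of PCP in children, and 3.1.3 rapid progression. No pre-symptomatic window is stated, so I assume 2, 4 or 8 weeks, onset unrelated to visit dates, and at most one episode per child. Coverage = window / interval. Expected PCP cases at the 24% of Table 6 are 0.24 × 200 = 48 in Group I and 0.24 × 120 = 28.8 in Group IIa, about 77 in all.

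| Window | Group I (52 weeks) | Group IIa (26 weeks) | Cases with a scheduled LDH in the window |
|---|---|---|---|
| 2 weeks | 2/52 = 3.8% | 2/26 = 7.7% | 1.8 + 2.2 = about 4 |
| 4 weeks | 4/52 = 7.7% | 4/26 = 15.4% | 3.7 + 4.4 = about 8 |
| 8 weeks | 8/52 = 15.4% | 8/26 = 30.8% | 7.4 + 8.9 = about 16 |

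With 4 to 16 cases, the 95% half-width on a sensitivity of 0.5 is 1.96 × 0.5/√n, or about 49 down to 24 percentage points (a rough approximation at such counts).

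**4. DTPA.** Sections 5.2.2, 5.2.4.5 and 8.2.4 all record the stop. Section 7.2 lists the test without a cut-off.

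**The case against.** The strongest reply is that 7.2 already confines O2 to detection before signs or symptoms, and nowhere says that illness-visit values will be pooled. Which visits count, the look-back window and the denominator can be left to an analysis plan. The markers are offered as likely to be useful, and accuracy is planned for each method, so scheduled SpO2, chest x-ray and lung function are not excluded. This stands in part: the text does not commit to pooling. It does not rescue PO2, because no choice of visits produces an arterial gas in a well child with normal oximetry.

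Several stronger readings are tempting and are not supported:

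- *PaO2 never precedes symptoms.* It can. Low or repeatedly indeterminate oximetry at a routine visit leads to a gas with no symptom required. Such values come only from oximetry screen-positives.
- *PCP without hypoxemia goes unconfirmed.* Under 5.2.3.1 and 5.2.3.2, lavage also follows non-response, worsening, starting TMP-SMX, and persistent or worsening radiographic change. Verification is partial, and how partial is unknown.
- *The 4 to 31% caps the sensitivity of LDH.* It is the chance that a scheduled sample falls in the window. It would be a ceiling only if every untested case were counted as a miss, which 7.2 does not say.
- *Every accuracy measure is flattered.* The verification mechanism pushes apparent specificity down.
- *DTPA is lost to O2.* Recruitment began in May 1990 (Appendix 1), so earlier scans can be analysed.

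**Conclusion.** The point holds for the PCP and early-lung-disease part of O2. Of the named markers, PaO2 cannot yield specificity or negative predictive value in symptom-free children with normal oximetry; this follows from the testing rules alone. Verification by lavage depends partly on oxygenation, which tends to raise apparent sensitivity and lower apparent specificity by an amount the document does not allow one to size. Scheduled LDH would cover roughly 4 to 15% of PCP cases in Group I and 8 to 31% in Group IIa before symptoms. Those figures rest on the assumed 2 to 8 week window and on onset unrelated to visits. DTPA needs a data cut-off.

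A reader might infer that O2 as a whole would get a falsely favourable answer. The document does not support that. IgG and the cardiac measures are scheduled tests and are not affected.

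**What to change.** Amend 7.2 for the lung part of O2:

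- **(a)** Use tests from scheduled visits at which no symptom or physical sign listed in 5.2.3.1 is present. An abnormal test result alone does not exclude a visit. The outcome is a Table 13 diagnosis before the next scheduled visit, and all such visits form the denominator.
- **(b)** Use scheduled SpO2 as the pre-symptomatic oxygenation measure. State that saturation below 96% itself triggers evaluation, so verification is still partial, and that the oximeter overestimates saturation below 96% (5.2.4.3). Carry this as a caveat or add a sensitivity analysis for partial verification.
- **(c)** Report PaO2 or A-a gradient and illness-visit LDH separately, as diagnostic accuracy among symptomatic or screen-positive children who had BAL. For scheduled LDH, report how many PCP cases had a sample before symptoms.
- **(d)** Limit DTPA to scans done before 10 February 1993.

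The cost is wording only, with no new test or visit. The price is fewer evaluable values, less precise estimates, and reliance on SpO2 where 5.2.4.3 regards the arterial gas as the more sensitive measure.
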